19.0 Provisions to Protect the Privacy Interests of Subjects

- 19.1 All participant data will be de-identified and linked to unique study PIDs. Personally identifiable information (names, emails, phone numbers) will be stored separately in a password protected file in Stronghold. Only authorized study personnel will have access to these files. Links for the Qualtrics survey will be tailored to each participant's PID, eliminating the need for participants to provide any identifying information. Furthermore, all study data collected through Expiwell will only be linked to each participant's PID.
- 19.2 Participants will be informed that the study data collected will remain confidential and that they may skip any questions or withdraw from the study at any time without penalty. Study staff will use neutral, supportive language during participant interactions and provide clear explanations of procedures. Sensitive topics will be discussed with nonjudgement, and participants will have access to resources and support if needed (e.g., mental health resources).
- 19.3 The research team's access will be restricted to team members who have signed confidentiality agreements, including PIs, project managers, research coordinators, and interviewers. Only these authorized personnel will access deidentified datasets and qualitative transcripts. Access to

identifiable information will be managed through Stronghold, which will be used for scheduling interviews or follow-up, will be strictly controlled and limited to necessary staff.

20.0 Compensation for Research-Related Injury

20.1 N/A

20.2 N/A

21.0 Economic Burden to Subjects

21.1 Participation in this study is not expected to impose economic costs on the participants. There can be instances where participants will want to download data-heavy materials from the application. We will encourage them to download these materials in a wifi-supported environment.

22.0 Consent Process

22.1 Informed consent will be an ongoing process. Participants will first be presented with the IRB-approved ICF at the time of initial online screening, which will describe the purpose of the study, procedures to be followed, and the risks and benefits of participation. They will have the option to download and save the ICF and will also be prompted to click through the ICF text in full, displayed on multiple screens in Qualtrics. Consent will be documented electronically within the Qualtrics survey; participants must confirm electronically that they have read and understood the ICF before beginning study activities. The consent process will continue into the Screening Zoom Interview, where a trained research staff member will review the ICF with the participant and answer any questions they might have (also see section 10.1).

23.0 Process to Document Consent in Writing

23.1 Consent will be documented electronically within the Qualtrics survey; participants must confirm electronically that they have read and understood the ICF before beginning study activities.

23.2 The research presents no more than minimal risk of harm to participants and involves no procedures for which written documentation of consent is normally required outside of the research context. Waiver to obtain written documentation of consent is requested.

23.3 A copy of the Informed Consent Form is attached, under file name "Informed consent form_GEM.docx".

24.0 Setting

24.1 To fully leverage the potential of mobile health interventions, we will use a national, remote recruitment and participation strategy using social media, online communities, contact with community-based organizations and universities. All procedures, including study onboarding, data collection, intervention delivery, and exit interviews, will be conducted virtually. This remote model enables accessibility across geographic backgrounds.

A community advisory board (CAB) will be formed and be asked to provide input in all stages of research, including informing study protocol, facilitating

results interpretation, and disseminating study findings. The CAB will meet regularly (monthly/biweekly depending on study phase). Two CAB members will be selected and recommended as co-chairs through CAB group discussion, and they will be responsible for preparing meeting agendas and providing a discussion summary to the research team. The investigative team will be present at the start of the CAB, and a team member (e.g., study coordinator) will attend CAB meetings as needed (e.g., to present the measurement package and solicit feedback). Consistent with our team's practice, members will be compensated for their time, and we will involve CAB in dissemination (e.g., co-writing certain products, authorship and/or acknowledging their contributions in papers, summary reports, etc.) as a capacity building activity.

25.0 Resources Available

25.1 The research team will have full access to the Brown School of Public Health's facilities and core resources, including dedicated office space at [name], data management support, and access to any additional necessary tools and infrastructure. The feasibility of recruiting 44 participants within 2 months is made possible through the team's past experiences and subsequent development of rigorous protocols regarding outreach (via social media, online communities, universities, and 300+ community-based organizations from previous research). The study is expected to be completed within a one-year period from the start date. Brown University IRB will be notified after study completion. This notification will include a final report summarizing the study findings, protocol adherence and other related documents. Any protocol deviations will be recorded and reported promptly. Oversight of internal monitoring of the participants' safety will be conducted by the PI, [name], who is a licensed psychologist. Researchers involved in this study will receive appropriate training regarding study procedures from team members with experiences conducting clinical trials and have their CITI training completed before beginning the study.

26.0 Multi-Site Research

26.1 N/A

26.2 N/A

Analytic Plan

V1_3.9.2026

Indicator	Benchmark Target
Recruitment	> 60% of eligible and approached participants enroll in the study.
Retention	> 70% retention of enrolled participants (complete final T2 post-intervention assessments).
Intervention Acceptability	> 75% of participants report a score of 24 or more on the Client Satisfaction Questionnaire (CSQ-8), indicating "good" satisfaction.
EMA Adherence	> 50% of participants complete 50% of the daily EMA prompts.
Audio Module Adherence	> 60% of participants complete 50% of the weekly audio modules for 4 weeks.

We will apply predefined benchmarks (see above) to assess the primary outcomes of feasibility and acceptability. Scores from the CSQ-8 and Session Evaluation Form (SEF) will be calculated and summarized using descriptive statistics (means, standard deviations, frequencies). Adherence will be calculated objectively via system-captured app data: EMA compliance will be calculated as the proportion of completed prompts out of total expected prompts, and audio compliance as the proportion of modules played to completion. Engagement outcomes will summarize completion of audio modules, use of meditation recordings/practices, and engagement in EMI.

Qualitative Exit Interviews To contextualize the quantitative acceptability data, semi-structured exit interviews will be conducted at T2 to explore: (a) perceived relevance, usability, and content preference of the audio modules, along with weekly peer sessions; (b) participant experience with the burden and frequency of the daily EMA prompts (3–4 per day) and the weekly audio volume (5–10 per week); (c) feedback on the module delivery (e.g., preference for batch release vs. daily drip); (d) perceived impact of the GEM intervention on daily target behaviors (mood) and depression/anxiety prevention; and (e) suggestions for content adaptation, pacing, and refinement to reduce participant burden in future efficacy trials.

Pre-Post Changes (Clinical Outcomes) As a single-arm trial, we will use repeated measures ANOVA to assess preliminary changes in the primary clinical targets of depression (e.g., measured via PHQ-9) and anxiety (e.g., measured via GAD-7) from T1 to T2 (and T3 follow-up), characterizing within-group effect sizes using Cohen's *d*. To model individual clinical trajectories, we will use mixed-effects modeling with time entered as a fixed effect and participant as a random effect, incorporating relevant baseline covariates (e.g., age, gender, ELA severity).

EMA/Longitudinal Data Analysis

We will leverage the high-density EMA data using linear mixed-effects models to assess within-person, day-to-day, and moment-to-moment associations. Specifically, we will use time-lagged

analyses to evaluate the immediate, temporal impact of intervention engagement. For example, we will model whether the completion of an audio module at time t predicts significant reductions in momentary negative affect, anxiety, or perceived stress at the subsequent EMA prompt (time $t+1$). Additionally, we will visualize the interrelations between momentary stress, engagement with audio modules, and subsequent mood fluctuations via temporal network models.

To assess **momentary mechanisms**, we will utilize 1-1-1 Multilevel Structural Equation Modeling (MSEM). We will test whether momentary activation of specific psychological states (e.g., interoception, cognitive defusion, or acceptance/willingness) measured immediately post-EMI significantly mediates the relationship between EMI engagement at time t and reductions in negative affect at the subsequent EMA prompt (time $t+1$). We will conduct mediation analysis to understand which mechanism carries the largest indirect effect on symptom reduction. Additionally, we will visualize the interrelations between daily stressors, momentary mechanism activation, and subsequent mood fluctuations via temporal network models.

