In addition to the weekly modules, participants will take part in a weekly, 1-hour "Group practice and connect" session on Zoom. The online sessions will comprise a cohort of 5-10 participants (depending on recruitment) and will be led by a research assistant, who has previous experiences with mindfulness programs as well as lived experiences of early life adversity. During each session, participants will be invited to participate in a group practice and reflection and to join group discussions on experiences regarding past week's practice. In the contact form (which is completed after the consent form), participants will be presented with the day and time of weekly sessions for the next two cohorts and asked to choose the times they are available for. If the participant is not available for either of the offered times, they will be marked as "deferred enrollment" in our participant tracking spreadsheet. A study RA will follow up with information about future cohort scheduling as that information becomes available.

Ecological momentary assessments and interventions: Over the first 4 weeks of the intervention period (i.e., Recommended Modules), participants will also complete 3 EMAs + EMIs per day through Expiwell. EMA and EMI will be delivered concurrently; the EMA will collect participant's response on their current mood, recent stressful experience, and type of stressor; participants will then receive a list of mindfulness exercises, which will be tailored to the type of stressor/emotion they will have indicated. The last EMA of the day will also include an option for the participants to submit a voice recording, serving as a "daily journal" at the end of the day to understand participant's daily experiences, including daily stressors and mindfulness practice application. To mitigate the risk of recording third-party participant voices, participants in the study will be

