Data analysis: Feasibility, acceptability, and preliminary effects will be assessed using data from the T1, T2, and T3 surveys as well as EMA responses. Qualitative data analysis will also be performed for the exit-interviews and voice recordings to further qualify our findings after transcription and deidentification. Exit interviews will be transcribed using Dedoose (already vetted through OIT), while EMA voice recordings will be transcribed automatically through Expiwell's AWS service. Additionally, recruitment and retention rates, completion of weekly modules, adherence to daily EMA and EMI prompts, weekly session attendance, and other engagement metrics from the application (e.g., frequency of EMI-triggered vs. self-initiated practice use, time spent in modules) will be used to inform study and intervention feasibility.

- 6.3 We will take all reasonable precautions to prevent adverse events to participants. As a meditation-based intervention, a number of actions have been taken to minimize meditation-related risks at different stages of the study. During the pre-enrollment stage, individuals with severe mental

illness that could preclude regular class attendance or impact group participation (i.e., symptomatic, untreated bipolar disorder or a history of psychosis and/or schizophrenia) are excluded from the study. During treatment, meditations are created to be relatively short and interspersed with dyads and reflections to minimize probability of risk. Developing strategies for working with physical and emotional discomfort is also an explicit goal of the program.

No drugs will be administered as part of this study. The only devices used are a) the participant's personal cell phone with the intervention content loaded through the Expiwell app and b) a wearable device Fitbit, which is commercially available and FDA-cleared for general wellness monitoring; it will be used solely to collect sleep and physiological data.

For all assessments and guides used for data collection, please refer to the document named "Compiled measures_GEM.docx".

6.4 A list of all data that and how they will be collected during the study is listed below:

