11.0 Vulnerable Populations

11.1 N/A

12.0 Local Number of Subjects

12.1 We anticipate enrolling 44 *participants in the single-arm trial*.

12.2 A larger number of young adults will be screened for eligibility, and 44 participants will be recruited to enroll in the single-arm trial. From these 44 participants, we aim to have at least 35 participants (i.e., approximately 80%) who complete all intervention procedures and follow-up assessments. Screening more participants ensures that we can meet the target enrollment despite ineligible candidates, and enrolling more ensures that we collect enough data points even with potential withdrawals.

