16.2 N/A

17.0 Data Management and Confidentiality

17.1 Quantitative data will be analyzed using a combination of descriptive and inferential statistics. Feasibility and acceptability data (e.g., CSQ-8 and SEF scores, proportion of completed EMA prompts, engagement metrics such as weekly practice rates and frequency of practice use) will be summarized using means and standard deviations. Preliminary effects on other primary, secondary, and exploratory outcomes (e.g., depression, anxiety, sleep quality, emotion regulation, mindfulness) will be evaluated using repeated measures analyses, such as mixed-effects models, to characterize effect sizes (e.g., Cohen's *d*). We will use mixed-effects modeling with time as fixed effect and participant as random effect to model trajectories, incorporating baseline covariates, to account for within-subject correlations across time points. EMA data will be analyzed using mixed-effects models to assess within-person day-to-day associations between stress and intervention engagement.

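### The SAP takes Cohen's d for PHQ-9 and GAD-7 from a repeated measures ANOVA, which by default drops incomplete participants; a mixed model that includes the weekly scores is the better source

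*SAP*

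**What the plan says.** **Estimator.** In the SAP, under Pre-Post Changes (Clinical Outcomes), "we will use repeated measures ANOVA to assess preliminary changes in the primary clinical targets of depression" and anxiety "from T1 to T2 (and T3 follow-up), characterizing within-group effect sizes using Cohen's" *d*. The next sentence adds a mixed model (time fixed, participant random, baseline covariates) for individual trajectories. It does not link that model to *d* and does not say which occasions enter it. Protocol 17.1 says that preliminary effects "will be evaluated using repeated measures analyses, such as mixed-effects models, to characterize effect sizes".

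**Attrition.** Protocol 12.2 says that "44 participants will be recruited to enroll in the single-arm trial" and aims for "at least 35 participants (i.e., approximately 80%) who complete all intervention procedures and follow-up assessments". The SAP's retention benchmark is passed once more than 70% of those enrolled complete T2. Protocol 14.3 lets participants withdraw from some assessments and continue with others. Neither document says how missing outcomes are handled.

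**Weekly scores.** Under Protocol 6.2 (Weekly assessments), the full PHQ-9 and GAD-7 are collected in each of the first four weeks. Protocol 6.4 lists the weekly assessments as a source of preliminary-efficacy data. Protocol 6.2 (Data analysis) says only: "Feasibility, acceptability, and preliminary effects will be assessed using data from the T1, T2, and T3 surveys as well as EMA responses". The SAP's clinical-outcome paragraph does not mention weekly scores.

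**Cohorts.** Protocol 5.2 and 6.2 place participants in weekly group sessions of 5 to 10 people. No model in either document has a term for session cohort.

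**The concern.** The two documents name different methods for the same *d*, and the SAP's choice handles incomplete records worst. Classical repeated measures ANOVA needs a value at every visit in the model. A participant without T2 contributes nothing. If one ANOVA spans all three visits, a participant with T1 and T2 but no T3 is also lost from the T1-T2 change.

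The SAP calls depression and anxiety the primary clinical targets, and Protocol 6.1 says these analyses may inform later studies. The effect sizes and their precision are therefore what the clinical part of this pilot delivers. If those who leave differ on scores already observed, complete-case change is a biased estimate for the 44 enrolled. The size and sign of that bias depend on who leaves, so a later reader of *d* could not correct for it.

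**Working it through.** **1. The plan's own attrition figure.** 35/44 = 79.5% and 0.80 × 44 = 35.2, so the protocol's figure of about 80% reproduces. For the T2 benchmark, 0.70 × 44 = 30.8, so the smallest passing count is 31. Possible exclusions: 44 − 35 = 9 and 44 − 31 = 13. The 31 refers to T2 only; further loss at T3 would remove more from a three-visit ANOVA.

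**2. Precision lost to complete-case analysis.** Assume all 44 have T1, equal SD σ at T1 and T2, and T1-T2 correlation ρ of 0.50 to 0.65 (not in the documents). With n₂ participants at T2 and n_c complete:

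- complete-case variance of change = 2σ²(1 − ρ)/n_c
- likelihood variance = σ²[(1 − ρ)²/44 + (1 − ρ²)/n₂]. This is a large-sample form that uses no weekly data.

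| Pattern | ρ | Complete-case | Likelihood | SE ratio |
|---|---|---|---|---|
| 35 complete, 9 missing T2 and T3 | 0.50 | 0.02857 | 0.02711 | 1.03 |
| same | 0.65 | 0.02000 | 0.01928 | 1.02 |
| 40 with T2, 35 complete | 0.50 | 0.02857 | 0.02443 | 1.08 |
| same | 0.65 | 0.02000 | 0.01722 | 1.08 |
| 31 complete, 13 missing T2 and T3 | 0.50 | 0.03226 | 0.02988 | 1.04 |
| same | 0.65 | 0.02258 | 0.02141 | 1.03 |

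Variances are in units of σ². At the target of 35 completers, the complete-case SE is about 2-8% larger. Compared with full data on 44, the SE factors are √(44/35) = 1.12 and √(44/31) = 1.19, but most of that loss comes from attrition itself, not from the ANOVA.

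**3. Bias.** Large-sample simulation (100,000 records). All inputs are assumptions: PHQ-9 mean falling from 11 to 8 (true change −3.00), SD 4.5, T1-T2 correlation 0.58, week-4-T2 correlation 0.71, and retention 70% or 80%. Where dropout depends on a score, the odds ratio is 2 or 3 per SD. Those who drop out miss both T2 and T3 but have all weekly scores.

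| Dropout depends on | Complete cases | Mixed model, T1-T3 | Mixed model with weekly scores |
|---|---|---|---|
| nothing | −3.00 to −3.01 | −3.00 to −3.01 | −3.00 to −3.01 |
| baseline score | −2.49 to −2.76 | −3.01 to −3.02 | −3.00 to −3.02 |
| week-4 score | −3.06 to −3.11 | −3.21 to −3.45 | −2.99 to −3.01 |
| T2 score itself | −3.25 to −3.53 | −3.40 to −3.86 | −3.27 to −3.59 |

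In the baseline rows the complete-case error is 0.24 to 0.51 points towards no change. *d* is 2.49/4.5 = 0.55 to 2.76/4.5 = 0.61, against a true 3.00/4.5 = 0.67. In the week-4 rows the error is 0.06 to 0.11 points away from no change. There, a mixed model limited to T1-T3 does worse than complete cases, and adding the weekly scores removes the bias.

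**4. Session cohorts.** 44/10 = 4.4 and 44/5 = 8.8, so cohorts of 5 to 10 mean 5 to 8 cohorts, averaging 44/8 = 5.5 to 44/5 = 8.8 people. The SE factor is √[1 + (m − 1) × ICC], where ICC is the within-cohort correlation of change. At an assumed ICC of 0.05 this is √1.225 = 1.11 to √1.39 = 1.18; at ICC 0 it is 1.0. The documents give no ICC.

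**The case against.** The strongest reply is that the SAP already contains a mixed model, that the protocol's wording is broad enough to cover an ANOVA, and that these outcomes are exploratory. All three are true. But the SAP gives the mixed model a different job, so *d* still comes from the ANOVA. The limited stakes bear on urgency; they do not make the ANOVA the better choice when the alternative costs so little.

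Several stronger readings are tempting, and the documents do not support them:

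- *The ANOVA gives biased estimates.* Only under some dropout patterns. There is no bias if dropout is completely random, and no method tried here is unbiased if dropout follows the unseen T2 score. Nor is replacing the ANOVA with a T1-T3 mixed model a full remedy, as the week-4 rows show.
- *The precision loss is 13-14%.* That arises with 26-29 complete cases, fewer than the 35 the protocol aims for. The 70% benchmark is a pass mark, not a forecast.
- *T1-T2 pairs are certain to be lost when only T3 is missing.* The SAP does not say whether it fits one three-visit ANOVA or separate comparisons.
- *The mixed model gives everyone the same slope, or excludes the weekly scores.* The SAP names participant as random without saying intercept only, and lists no occasions for that model. It is silent on both.
- *Ignoring cohorts makes the intervals wrong.* Only if change is correlated within cohort. A cohort effect constant over time cancels in a pre-post difference. The omission applies equally to the mixed model, so it is no argument against the ANOVA in particular.

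**Conclusion.** The point holds as a cheap improvement that should be made. The SAP ties *d* to a method that by default excludes incomplete participants, where the protocol's example is mixed models. No missing-data rule is stated, and the weekly PHQ-9 and GAD-7 scores have no named place in the analysis.

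Within the plan's own targets, 9 to 13 of 44 participants may be excluded. The SE penalty against likelihood estimation is about 2-8% at the target of 35 completers. Bias in mean change is about 0.1 to 0.5 PHQ-9 points, in either direction, when dropout follows baseline or week-4 scores, and nil when it is completely random. The attrition counts come from the documents; the SD, correlations, dropout strengths and ICC are assumptions. The benefit of the weekly scores is a best case, because the simulation has them complete in those who later drop out. The feasibility and acceptability benchmarks do not change.

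**What to change.** Make one likelihood-based mixed model, fitted to all enrolled participants, the source of the clinical-outcome estimates, and align SAP and Protocol 17.1 on it:

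- Put T1, Weeks 1-4, T2 and T3 scores in the outcome vector, with time categorical.
- State the covariance structure and a fallback. An unstructured matrix over seven occasions has 7 × 8/2 = 28 parameters, which is many for 44 people.
- State the missing-at-random assumption.
- Report T1-T2 and T1-T3 changes in scale points with 95% CIs, and derive *d* from them with a named SD.
- Drop the ANOVA or keep it as secondary.
- Add a sensitivity analysis for session cohort, such as small-sample cluster-robust SEs or the SE recalculated over a stated range of ICC.

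The cost is a few lines of SAP text and a little programming. Intervals may widen once cohorts are considered, and a cohort variance estimated from 5 to 8 cohorts will be imprecise, which is why cohort belongs in a sensitivity analysis. No new data are needed.

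### The SAP takes the PHQ-9 and GAD-7 change and Cohen's d from a repeated measures ANOVA, which uses only participants with every visit entered; the mixed model already planned would keep the partial records

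*SAP*

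**What the plan says.** The SAP section on pre-post changes in clinical outcomes has two analyses of the same outcomes.

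- **ANOVA.** "we will use repeated measures ANOVA to assess preliminary changes in the primary clinical targets of depression" (PHQ-9) and anxiety (GAD-7), "from T1 to T2 (and T3 follow-up), characterizing within-group effect sizes using Cohen's" *d*. T3 stands in brackets. The text does not say whether it is a third level of one ANOVA or a separate comparison.
- **Mixed model.** For individual trajectories, "we will use mixed-effects modeling with time entered as a fixed effect and participant as a random effect", with baseline covariates. No effect size is attached to this model.

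Protocol section 17.1 says that preliminary effects "will be evaluated using repeated measures analyses, such as mixed-effects models, to characterize effect sizes". It does not name ANOVA.

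On losses, protocol section 12.2 says that "44 participants will be recruited to enroll in the single-arm trial" and that "we aim to have at least 35 participants (i.e., approximately 80%) who complete all intervention procedures and follow-up assessments". The SAP benchmark table sets "> 70% retention of enrolled participants (complete final T2 post-intervention assessments"). Neither document gives a missing-data rule for these outcomes, defines the analysis set, or ranks the ANOVA against the mixed model.

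**The concern.** A classical repeated measures ANOVA deletes any participant who lacks one of the visits entered. With T1, T2 and T3 as levels, someone seen at T1 and T2 but not at T3 would drop out of the T1-T2 contrast too. That wastes observed data. It also biases the contrast if the chance of missing T3 depends on how the participant was doing at T2. A likelihood-based model keeps the partial record and handles loss that depends on observed scores.

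What is at stake is the reported size of the within-group change. The SAP calls depression and anxiety its primary clinical targets, and protocol section 6.1 intends the preliminary outcomes to inform later studies, so a d that is too large or too small could mislead the planning of the next trial. With two unranked analyses of one outcome, the choice between them could also be made after the data are seen.

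**Working it through.** **1. The plan's own figure.** 35/0.80 = 43.75, rounded up to 44, and 35/44 = 79.5%. The enrolment figure reproduces. The documents state no alpha, power or target effect, so there is no power figure to check.

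**2. Who contributes.**

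- Completion target: 35 of 44, so up to 44 - 35 = 9 (20%) are dropped under the three-level reading.
- T2 benchmark floor: 0.70 × 44 = 30.8, so 31 of 44 at T2. With an assumed further 15% loss at T3, 31 × 0.85 = 26.4, about 26. About 5 people with both T1 and T2 scores, and 13 with T1 only, are dropped.
- Separate T1-T2 analysis: only those without T2 are lost, which is 44 - 31 = 13 at the floor. Missing T3 then removes nothing from T1-T2.

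**3. Assumptions not in the documents.** PHQ-9 SD at T1 4.1; T1-T2 correlation 0.44; true T1-T2 change -3.0; T2 loss random. The T2 SD matters and is varied: 4.1 and 5.

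**4. Precision when loss is unrelated to outcome (benchmark floor).** SD of change = √(SD1² + SD2² - 2 × r × SD1 × SD2); SE for complete cases = SD of change/√n.

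- T2 SD 4.1: √(16.81 + 16.81 - 14.79) = 4.34. Complete cases, n = 26: 4.34/√26 = 0.85. Likelihood model on all records: about 0.75. Ratio 0.85/0.75 = 1.13.
- T2 SD 5: √(16.81 + 25 - 18.04) = 4.88. Complete cases: 4.88/√26 = 0.96 (0.95 in simulation). Likelihood model: 0.86. Ratio 0.95/0.86 = 1.10 to 0.96/0.86 = 1.12.

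So the SE is about 11-13% larger, with no bias. Under the separate T1-T2 reading with T2 SD 4.1, the paired SE is 4.34/√31 = 0.78 against about 0.75-0.76, a small loss.

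**5. Bias when T3 loss depends on the T2 score (three-level reading).** Trials of 44 were simulated, with the log-odds of missing T3 linear in the T2 score at 0.15 per point. That is e^(0.15 × 5) = 2.1-fold per 5 points. The true change is -3.0.

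| Setting | T2 SD | Complete cases | Likelihood model | Error of complete cases |
|---|---|---|---|---|
| Floor, worse T2 scorers leave | 4.1 | -3.20 | -3.00 | 0.20/3.0 = 7% over |
| Floor, worse T2 scorers leave | 5 | -3.33 | -3.00 | 0.33/3.0 = 11% over |
| Floor, better T2 scorers leave | 4.1 | -2.80 | -3.00 | 0.20/3.0 = 7% under |
| Floor, better T2 scorers leave | 5 | -2.65 | -2.99 | 0.35/3.0 = 12% under |
| About 35 complete, worse T2 scorers leave | 5 | -3.26 | -3.01 | 0.26/3.0 = 9% over |

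**6. Cross-check under other assumptions.** In SD units, with a true change of -0.40, correlation 0.6, and T1 and T2 fully observed, complete cases gave -0.45 to -0.48 with 20% T3 loss and -0.48 to -0.51 with 30% loss (odds of loss 2- to 3-fold per SD worse at T2). They gave -0.40 when loss was unrelated to outcome, and -0.35 when better scorers left (20% loss, 2-fold). The likelihood model stayed between about -0.40 and -0.42 throughout. The T1-T3 estimate was not biased in this set-up.

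**The case against.** The strongest reply is that the remedy is already in the plan. The mixed model follows in the next sentence, and protocol 17.1 ties mixed models to effect sizes. That is right about cost, but it does not settle which result is reported: the SAP attaches d to the ANOVA and ranks nothing.

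Four stronger readings are tempting, and the documents do not support them.

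- **T3 loss certainly deletes T1-T2 data.** A reader might infer this, but T3 is in brackets. With a separate T1-T2 analysis the bias in step 5 is zero. The three-level reading is natural, since a two-visit repeated measures ANOVA is simply a paired t-test, but it is not stated.
- **The SAP contradicts the protocol.** Protocol 17.1 gives mixed models as an example, and an ANOVA is also a repeated measures analysis. The two documents differ in emphasis; this is not a clear departure.
- **The plan forecasts 20-30% loss.** The protocol's 35 of 44 is a target for completers, and "> 70% retention of enrolled participants" is a feasibility pass mark, not a prediction. The 26 of 44 setting adds an assumed T3 loss to that pass mark.
- **The improvement will be overstated.** No document says who will drop out. The error can run either way or be zero.

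It is also fair to say that a bias of 0.20-0.33 points is well below the SE of 0.85-0.95 in a trial of this size.

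**Conclusion.** The point holds in a limited form. The SAP attaches the PHQ-9 and GAD-7 change and d to the method that cannot use partial records, leaves the place of T3 open, and does not say which of its two models supplies the reported effect.

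Under the three-level reading, about 35 of 44 contribute at the completion target, and about 26 at the benchmark floor with 15% further T3 loss. In the latter setting the cost is an SE about 11-13% larger if loss is unrelated to outcome. If the odds of missing T3 change 2.1-fold per 5 PHQ-9 points at T2, the change is misstated by roughly 7% (T2 SD 4.1) to 11% (T2 SD 5), upwards if worse scorers leave and downwards by a similar amount if better scorers leave. These sizes rest on the assumed SDs, correlation, true change and loss pattern. Under a separate T1-T2 analysis, T3 loss has no effect on that contrast.

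Severity is moderate. Although preliminary efficacy is part of the primary objective, the SAP's primary outcomes are feasibility and acceptability, protocol 6.1 treats the preliminary outcomes as exploratory, and no benchmark or decision rule depends on this d.

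**What to change.** Rewrite the SAP paragraph as follows.

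- The T1-T2 and T1-T3 changes in PHQ-9 and GAD-7, and Cohen's d with its standardising SD named, come from the likelihood-based mixed model, with 95% confidence intervals.
- Visit is a categorical fixed effect, and all available T1, T2 and T3 records of all enrolled participants are used.
- The number contributing at each visit is reported.
- The ANOVA is dropped, or kept as a labelled complete-case sensitivity analysis that states which visits it includes.

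This settles the model, the role of T3 and the handling of missing visits together, and brings the SAP closer to protocol 17.1. It costs one paragraph. The mixed model is already planned, and no new data or visits are needed.
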